6.1.1 Investigational Drug

6.1.1.1 Pomalidomide Description

Pomalidomide, 4-amino-2-(2, 6-dioxo-3-piperidyl) isoindoline-1'-one)-1, 3-dione, belongs to the IMiD class of compounds. The Chemical Abstract Service (CAS) registry number for Pomalidomide is 19171-19-8. The chemical structure of the active pharmaceutical ingredient (API) is as follows:

Pomalidomide has an asymmetric carbon atom and can therefore exist as the optically active forms S (-) and R (+). Pomalidomide has been developed as a racemate.

6.1.1.2 CLINICAL PHARMACOLOGY

Mechanism of Action:

Pomalidomide, a thalidomide analogue, is an immunomodulatory agent that, among other anti-tumor properties, on an equimolar basis in vitro, displays equivalent anti-angiogenic activity, about 8-fold greater activity in stimulation of apoptosis, at least 10-fold greater activity in inhibition of cellular COX-2 production and over 4,000-fold greater activity in inhibition of cellular TNF-alpha production relative to thalidomide [9,10]. Pomalidomide has also been shown to stimulate antibody-dependent cytotoxic T-cell activity (ADCC) [11].

6.1.1.3 Dose and tolerability:

Pomalidomide was safe at doses of up to 50 mg in a phase 1 single dose study in normal, healthy male volunteers and up to 5 mg QOD or 2 mg QD in a phase 1 multi-dose clinical study in subjects with relapsed or refractory multiple myeloma; DLTs seen in subjects receiving higher doses were predominantly hematopoietic (i.e., neutropenia), and lower grade, self-limited neutropenia was also seen in some of the 1 and 2 mg QD and 5 mg QOD recipients. In a multi-dose, phase 2 clinical study of subjects with prostate cancer, 2 mg QD dosing was well tolerated and, unlike the multiple myeloma subjects who received 1 and 2 mg QD doses, only an overall shift to lower neutrophil counts was noted. No clinically relevant neutropenic AEs were observed, and no grade 3 or 4 neutropenic events occurred. It is, therefore, likely that subjects with solid tumors that do not extensively involve the bone marrow will have a higher pomalidomide MTD than subjects with hematologic malignancies.

6.1.1.4 Supplier(s)

Celgene Corporation will supply pomalidomide.

6.1.1.5 Dosage form

Pomalidomide will be supplied as 0.5 mg, 1.0 mg, and 2.0 mg capsules for oral administration.

6.1.1.6 Packaging

Pomalidomide will be shipped to the pharmacy at the study site in individual bottles. Bottles will contain a sufficient number of capsules to last for one cycle of dosing. Study drug must be dispensed in the original packaging with the label clearly visible.

6.1.1.7 Labeling

Pomalidomide investigational supplies are dispensed to the patients in individual bottles of capsules. Each bottle will identify the contents as study medication. In addition, the label will bear Celgene's name, quantity contained and the standard caution statement as follows: Caution: New drug - Limited by Federal law to investigational use. Pomalidomide should not be handled by FCBP unless wearing gloves. All bottles will contain the following warning label: "WARNING: POTENTIAL FOR HUMAN BIRTH DEFECTS."

The study drug label must be clearly visible. Additional labels must not cover the Celgene label.

6.1.1.8 Receipt of study drug

The Investigator or designee is responsible for taking an inventory of each shipment of study drug received, and comparing it with the accompanying study drug accountability form. The Investigator will verify the accuracy of the information on the form, sign and date it, retain a copy in the study file, and return a copy to Celgene or its representative.

6.1.1.9 Storage

At the study site, all investigational study drugs will be stored in a locked, safe area to prevent unauthorized access.

The study drug should be stored at room temperature away from direct sunlight and protected from excessive heat and cold.

6.1.1.10 Unused study drug supplies

Any unused study drug is to be disposed of as per UTMDACC institutional policy. If any study drug is lost or damaged, its disposition should be documented in the source documents. Patients will be instructed to return empty bottles or unused capsules.

6.1.1.11 Drug dispensing requirements

In investigational studies, pomalidomide will be dispensed through a qualified healthcare professional (including but not limited to, nurses, pharmacists and physicians). These healthcare professionals will be trained by Celgene in requirements specific to counseling of subjects. Once trained, these healthcare staff will counsel subjects prior to medication being dispensed to ensure that the subject has complied with all requirements including use of birth control and pregnancy testing (FCBP) and that the subject understands the risks associated with pomalidomide. This step will be documented with a completed Education and Counseling Guidance Document (Appendix B), and no drug will be dispensed until this step occurs. Counseling includes verification with the patient that required pregnancy testing was performed and results were negative.

A Pomalidomide Information Sheet (Appendix C) will be supplied to the patient each time that pomalidomide is dispensed.

Pomalidomide (POMALYST[®]) will be provided to research subjects for the duration of their participation in this trial at no charge to them or their insurance providers. Pomalidomide will be provided in accordance with the Celgene Corporation's POMALYST REMS[™] program. Per the standard **POMALYST REMS[™]** program requirements, all physicians who prescribe pomalidomide for research subjects enrolled into this trial, and all research subjects enrolled into this trial, must be registered in and must comply with all requirements of the **POMALYST REMS[™]** program.

Only enough pomalidomide capsules for 1 cycle of therapy may be provided to the patient each cycle.

6.2 Screening and Eligibility

The Investigator is responsible for keeping a record of all subjects who sign an Informed Consent Form for entry into the study. All subjects will be screened for eligibility. Screening procedures are outlined in Section 2, *Schedule of Study Assessments* and unless otherwise specified, must take place within 28 days prior to initiation of therapy.

Approximately 21 subjects with symptomatic Waldenström Macroglobulinemia will be screened for enrollment and must meet the eligibility criteria below.

6.2.1 Inclusion Criteria

Subjects must meet the following inclusion/exclusion criteria to be eligible for the study.

Inclusion criteria

1. Understand and voluntarily sign an informed consent form.
2. Age ≥ 18 years at the time of signing the informed consent form.
3. Able to adhere to the study visit schedule and other protocol requirements.
4. Waldenström's Macroglobulinemia that has relapsed and/or is refractory to at least one prior line of therapy
5. All previous cancer therapy, including radiation, hormonal therapy and surgery, must have been discontinued at least 4 weeks prior to treatment in this study.
6. ECOG performance status of ≤ 2 at study entry (see Appendix D).
7. Laboratory test results within these ranges:
 - Serum creatinine ≤ 2.0 mg/dL
 - Creatinine clearance ≥ 45 ml/min
 - Total bilirubin $\leq 3 \times$ Upper Limit of Normal (ULN) or Direct Bilirubin $\leq 2 \times$ ULN
 - AST (SGOT) and ALT (SGPT) $\leq 2 \times$ ULN
 - Platelet count ≥ 20 K/ μ L
 - Absolute neutrophil count ≥ 500 K/ μ L
8. Disease free of prior malignancies for ≥ 5 years with exception of currently treated basal cell, squamous cell carcinoma of the skin, or carcinoma *“in situ”* of the cervix or breast.
9. Females of childbearing potential (FCBP)[†] must have a negative serum or urine pregnancy test with a sensitivity of at least 25 mIU/mL within 10 – 14 days prior to

[†] A female of childbearing potential is a sexually mature woman who: 1) has not undergone a hysterectomy or bilateral oophorectomy; or 2) has not been naturally postmenopausal for at least 24 consecutive months (i.e., has had menses at any time in the preceding 24 consecutive months).

starting pomalidomide and must either commit to continued abstinence from heterosexual intercourse or begin TWO acceptable methods of birth control, one highly effective method and one additional effective method AT THE SAME TIME, at least 28 days before she starts taking pomalidomide. FCBP must also agree to ongoing pregnancy testing. Men must agree to practice complete abstinence or agree use a latex condom during sexual contact with a FCBP while participating in the study, during dose interruptions and for at least 90 days following study drug discontinuation, even if they have had a successful vasectomy. All patients must be counseled at a minimum of every 28 days about pregnancy precautions and risks of fetal exposure. See Appendix A Risks of Fetal Exposure, Pregnancy Testing Guidelines and Acceptable Birth Control Methods, AND also Appendix B: Education and Counseling Guidance Document

10. Able to take aspirin (325mg) daily as prophylactic anticoagulation (patients intolerant to ASA may use therapeutic dose warfarin or low molecular weight heparin).
11. All study participants must be registered into the mandatory POMALYST REMS™ program, and be willing and able to comply with the requirements of the POMALYST REMS™ program.

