6.2.2 Exclusion criteria

1. Any serious medical condition, laboratory abnormality, or psychiatric illness that would prevent the subject from signing the informed consent form.
2. Pregnant or breast feeding females. (Lactating females must agree not to breast feed while taking pomalidomide or for 28 days after stopping pomalidomide).
3. Any medical or psychiatric condition, including the presence of laboratory abnormalities, which places the subject at unacceptable risk if he/she were to participate in the study, or confounds the ability to interpret data from the study.
4. Use of any other experimental drug or therapy within 28 days of the first dose of study drug.
5. Known hypersensitivity to thalidomide or lenalidomide.
6. The development of erythema nodosum if characterized by a desquamating rash while taking thalidomide or similar drugs.
7. Any prior use of pomalidomide.
8. Concurrent use of other anti-cancer agents or treatments.
9. Known positive for HIV or acute hepatitis A or acute or chronic active hepatitis B or C.
10. Grade >2 peripheral neuropathy

11. Neutrophil count <1000K/ μ L and/or platelet count <100K/ μ L unless infiltration by Waldenström's Macroglobulinemia equals or exceed 60% of bone marrow cellularity.

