6.5 Instructions for initiation of a New Cycle

A new course of treatment may begin on the scheduled Day 1 of a new cycle if:

- The ANC is $\geq 1.0K/\mu L$, or \geq the baseline ANC, if the baseline ANC was $<1.0K/\mu L$.
- The platelet count is $\geq 100K/\mu L$, or \geq the baseline platelet count, if the baseline platelet count was less than $100K/\mu L$.
- Any drug-related rash, neuropathy or cardiac event that may have occurred has resolved to \leq grade 1 severity or baseline.
- Any other drug-related adverse events that may have occurred have resolved to \leq grade 2 severity.

If these conditions are not met on Day 1 of a new cycle, the subject will be evaluated weekly and a new cycle of treatment will not be initiated until the toxicity has resolved as described above. A maximum delay of 21 days is allowed for any given cycle. If these conditions remain unmet on Day 21, the patient is to be taken off of the protocol.

If anti-thrombotic prophylaxis (aspirin, else warfarin or low molecular weight heparin) was held during a given cycle for a platelet count $<50 K/\mu L$, it should be resumed as soon as the platelet count recovers to $\geq 50 K/\mu L$.

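### The neutrophil limits in inclusion 7 (500 K/µL) and exclusion 11 (1000K/µL) carry a unit error, and inclusion 7 as printed contradicts the cycle-start rule in Section 6.5

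*Combined protocol and SAP*

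**What the plan says.** Section 6.2.1, criterion 7, lists laboratory ranges for entry. The neutrophil line reads "Absolute neutrophil count ≥ 500 K" per µL; a separate line sets the platelet floor at 20 K/µL. The section opens with "Subjects must meet the following inclusion/exclusion criteria to be eligible for the study", and no exception is attached to criterion 7.

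Section 6.2.2, criterion 11, excludes patients with "Neutrophil count <1000K" per µL and/or platelets below 100K/µL. It waives this where infiltration by the disease "equals or exceed 60% of bone marrow cellularity".

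Section 6.5 sets the conditions for starting a new cycle. The neutrophil count must be at least 1.0K/µL, or at least "the baseline ANC, if the baseline ANC was" below 1.0K/µL. The platelet condition has the same form, with 100K/µL as the limit.

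**The concern.** The entry limits and the cycle-start limit concern the same laboratory value and are all printed in K/µL, yet they differ by factors of hundreds. Section 6.5 makes explicit allowance for patients who were enrolled with a neutrophil count below 1.0K/µL. Inclusion 7 as printed would have kept every one of them out.

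This is operative text that decides who enters the trial. The neutrophil count is also close to the primary endpoint. Section 4.2 reports neutropenia as the most common dose-limiting toxicity in an earlier myeloma study, and Section 6.4.1 counts Grade 4 neutropenia lasting 7 days or more as a DLT here. If staff silently correct the figure, entry rests on an interpretation that is written down nowhere, and a monitor or auditor has no valid printed limit to check against.

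**Working it through.** **Inputs**

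- Inclusion 7 (6.2.1): neutrophils ≥ 500 K/µL; platelets ≥ 20 K/µL; no exemption.
- Exclusion 11 (6.2.2): neutrophils < 1000K/µL and/or platelets < 100K/µL; waived if marrow infiltration is ≥ 60%.
- Cycle start (6.5): neutrophils ≥ 1.0K/µL and platelets ≥ 100K/µL, or the baseline value if that was lower.

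**Step 1: what K means here.** Section 6.5 gives the platelet limit for holding anti-thrombotic prophylaxis as 50 K/µL. Sections 6.4.2 and 6.6.1.1 give the platelet limit for the same prophylaxis as 50,000. So K = 50,000 / 50 = 1,000.

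**Step 2: the printed limits in full.**

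- Inclusion 7: 500 × 1,000 = 500,000/µL.
- Exclusion 11: 1000 × 1,000 = 1,000,000/µL.
- Section 6.5: 1.0 × 1,000 = 1,000/µL.

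**Step 3: ratios to Section 6.5.**

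- Inclusion 7: 500,000 / 1,000 = 500.
- Exclusion 11: 1,000,000 / 1,000 = 1000.
- Platelets in exclusion 11: 100K / 100K = 1.

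So within one criterion the platelet limit matches Section 6.5 exactly, and the neutrophil limit is off by exactly the value of K.

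**Step 4: what removing the K would do.** The limits would read 500/µL (0.5K/µL) and 1,000/µL (1.0K/µL). The second equals the Section 6.5 figure. The first lies below the second, as the platelet floor of 20 K already lies below the 100K in exclusion 11. This is arithmetic on the printed digits and does not establish the intended limits.

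**Step 5: who could enter on a literal reading.** The documents give no upper range for patients' neutrophil counts, so a wide range is assumed.

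| Assumed count (/µL) | Inclusion limit ÷ count | Exclusion limit ÷ count |
|---|---|---|
| 1,000 | 500 | 1000 |
| 10,000 | 50 | 100 |
| 100,000 | 5 | 10 |

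Every count in this range fails inclusion 7. Every count in it also triggers exclusion 11, unless the marrow exemption applies. Correcting inclusion 7 alone would therefore not be enough: exclusion 11 as printed would still confine entry to patients with at least 60% infiltration.

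**The case against.** The fair case against making much of this is that it is a recognisable slip. Section 6.5 pairs 1.0K with 100K for the same two cell counts that exclusion 11 prints as 1000K and 100K, so an attentive reader can see what happened. The inclusion figure is so implausible that accidental use as printed is unlikely. The documents include no checklist, case report form or deviation record showing that anyone applied it. A clarification query or a technical audit finding is the realistic outcome. All of that stands, and it limits the weight of the point. It does not make the printed criterion usable.

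Some stronger readings are tempting but not supported:

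- **That both limits are 1000 times the Section 6.5 value.** Only exclusion 11 is; inclusion 7 is 500 times. A 1000-fold excess for inclusion 7 holds only against 500/µL, which the documents never print.
- **That Section 6.5 contradicts both criteria.** The allowance for low baseline counts is compatible with exclusion 11, because patients may enter under the 60% marrow exemption. The direct contradiction is with inclusion 7.
- **That Section 6.5 proves the intended limits.** It shows only that the inclusion floor must lie below 1,000/µL if such patients are to be enrolled. An entry limit need not equal a cycle-start limit.
- **That all of up to 30 patients would be eligibility deviations.** This assumes literal application, for which the documents offer no evidence.
- **That neutropenia is the stated expected DLT in this disease.** The protocol reports it from myeloma. Section 6.4.5 says the listed class events are not necessarily expected.

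One could also argue that a patient might qualify at screening and have a lower baseline count on Day 1. To move from inclusion 7 as printed to below 1.0K/µL, the count would have to fall more than 500-fold within the 28-day screening window. That does not rescue the text.

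**Conclusion.** The point holds as a unit error in two eligibility criteria. The printed limits are 500,000/µL and 1,000,000/µL, which are 500 and 1000 times the cycle-start limit in Section 6.5. Inclusion 7 and Section 6.5 cannot both be followed as written. For exclusion 11 the evidence is the pattern of the figures, and it points to a stray K rather than to a logical contradiction.

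The statement that no patient meets inclusion 7 rests on two things: a literal reading, and the assumption that no patient reaches 500,000/µL. That assumption is comfortable, since even a count of 100,000/µL falls short by a factor of 5. The likely practical harm is to the traceability of eligibility decisions. Nothing here shows that the wrong patients would be enrolled. The correction is worth making because these are decision thresholds and the change is small.

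**What to change.** Correct the unit of the neutrophil limit in inclusion 7 and in exclusion 11, and reconcile both with Section 6.5 so that all three are in one unit. The sponsor should confirm the intended limits; this review does not propose values. Check the eligibility checklist and any data-entry range checks for the same figures, and correct them together with the protocol.

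The text change is one unit in two lines. It still needs an amendment: Section 9.1 requires the principal investigator's agreement, review and approval by the supporting company, and written IRB approval before use. The DLT definition, the 3+3 rules, the sample size and the analyses do not change.

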6.2.2 Exclusion criteria

1. Any serious medical condition, laboratory abnormality, or psychiatric illness that would prevent the subject from signing the informed consent form.
2. Pregnant or breast feeding females. (Lactating females must agree not to breast feed while taking pomalidomide or for 28 days after stopping pomalidomide).
3. Any medical or psychiatric condition, including the presence of laboratory abnormalities, which places the subject at unacceptable risk if he/she were to participate in the study, or confounds the ability to interpret data from the study.
4. Use of any other experimental drug or therapy within 28 days of the first dose of study drug.
5. Known hypersensitivity to thalidomide or lenalidomide.
6. The development of erythema nodosum if characterized by a desquamating rash while taking thalidomide or similar drugs.
7. Any prior use of pomalidomide.
8. Concurrent use of other anti-cancer agents or treatments.
9. Known positive for HIV or acute hepatitis A or acute or chronic active hepatitis B or C.
10. Grade >2 peripheral neuropathy

11. Neutrophil count <1000K/ μ L and/or platelet count <100K/ μ L unless infiltration by Waldenström's Macroglobulinemia equals or exceed 60% of bone marrow cellularity.

6.3 Visit schedule and assessments

Screening Assessments and all on-study scheduled visits and assessments are outlined in Section 2, *Table of Study Assessments*.

At treatment discontinuation, subjects will undergo off study evaluations as per the *Schedule of Assessments*, Section 2. In addition, a safety assessment will be done approximately 30 days after the last dose of study drug. Subsequently, subjects will be contacted by the site study coordinator at a minimum of every 6 months, until death or 12 months from the last dose of study drug administration, whichever occurs first. At these follow-ups, the study coordinator will collect information about cancer therapies administered after participation in this study (including dates of treatment), and for survival unless the patient withdraws consent. The information on subsequent treatment and survival status may be obtained without having the subject visit the study center (i.e. phone call). If the information is obtained by phone call then written documentation of the communication must be available for review in the source documents.

6.4 Drug Administration

6.4.1 Treatment assignments

This is a Phase I non-randomized study. Eligible patients will be allocated to treatment in the order in which they sign the informed consent and that all documentation needed to confirm eligibility has been completed. A maximum of 30 subjects will be enrolled and treated with single agent pomalidomide. Starting at dose level 1 in Schedule A, the study will enroll patients in cohorts of 3, following a standard 3 +3 statistical design. (see Section 11.0).

Definition of Dose Limiting Toxicity (DLT):

Toxicity will be evaluated according to the NCI CTCAE version 4.0, (see Appendix E)

1) Non-hematologic dose limiting toxicity (DLT) is defined as any grade ≥ 3 non-hematological toxicity occurring during the first 28 days (first cycle) of treatment, with the specific exception of:

- Isolated Grade 3 elevation of liver function tests (LFTs) without associated clinical symptoms, lasting for ≤ 7 days in duration.
- Isolated Grade 3 elevation of amylase without associated clinical symptoms
- Grade 3 hypocalcemia, hypokalemia, hypomagnesemia, hyponatremia, or hypophosphatemia which responds to medical intervention.

2) Hematological dose limiting toxicity is defined as Grade ≥ 3 neutropenia with fever ≥ 38.5 , Grade 4 neutropenia lasting for ≥ 7 days in duration, or any Grade 4 anemia or thrombocytopenia occurring during the first 28 days (first cycle) of treatment.

Definition of Maximum Tolerated Dose (MTD): MTD is defined as the highest dose level in which 6 patients have been treated with less than 2 instances of DLT.

